**ALLOB-DU1 - Clinical Study Protocol**

ALLOB-DU1_CSP	V 05	Author: [name]	February 02, 2017	Pg. 38/136
---------------	------	-------------	-------------------	------------

The Principal Investigator will then complete and sign the Case Report Form (Screening and Inclusion Visit pages), thereby attesting and recording that signed ICF has been obtained from the patient.

The study participant will be invited to date and sign any subsequent version of the ICF, as approved by the IEC. The Principal Investigator (or the person who conducted the Informed Consent discussion) will also sign and date the document on the same day.

### **2.3.2 Procedures**

#### **2.3.2.1 *ALLOB® Implantation Procedure***

Patients will undergo under anaesthesia (e.g., general, loco-regional or local as chosen by the Investigators) the implantation of ALLOB® with a trephine into the delayed-union site (single administration).

However, when necessary as per Investigator's judgement, the implantation of ALLOB® into the delayed-union site can be performed using two surgical approaches.

#### **2.3.2.2 *Rescue Surgery Procedure***

When judged necessary, the Principal Investigator can decide to perform a rescue surgery. The patient can be withdrawn from the study for a rescue surgical (e.g., bone autograft, allograft...) or non-surgical treatment according to the standard-of-care procedure of the investigating site.

Reason for rescue surgery, type and date will be recorded.

## **2.4 Patient Evaluation**

### **2.4.1 Definition of Delayed-union in the Study**

In this study, a delayed-union fracture is defined at the time of screening as (i) an absence of healing 3 months (with a maximum of 7 months)  $\pm$  2 weeks after the onset of fracture and (ii) an absence of the progression of healing over the last 4 weeks, as confirmed by clinical and radiological evaluation.

## ALLOB-DU1 - Clinical Study Protocol

ALLOB-DU1_CSP	V 05	Author: [name]	February 02, 2017	Pg. 39/136
---------------	------	-------------	-------------------	------------

#### 2.4.2 Clinical Evaluation

In order to avoid bias, clinical evaluation should be the first procedure during a study visit before discussing with the Investigator or the Study Nurse/Coordinator. Indeed, the patient has to complete the questionnaires alone without any outside intervention (Bryant and Fernandes, 2011).

The following clinical assessment will be evaluated:

- Global Disease Evaluation using a Visual Analogue Scale (see details in section 3.2.1 and Annex 1): the Global Disease Evaluation VAS is a 100 mm length horizontal line where 0 means best possible health status (“very well”) and 100 the worst possible health status (“extremely bad”). Patients must mark an “X” on the scale to indicate their general health status over the last week. Principal Investigator (or the study nurse) must mark an “X” on the scale to indicate the general health status of the patient as perceived at the time of the visit.
- Pain using a Visual Analogue Scale (see details in Annex 2): the Pain VAS is a 100 mm length horizontal line with endpoints labelled “no pain” (0) and “extreme pain” (100). Patients must mark an “X” on the scale to indicate their pain over the last week. In this study, pain will be evaluated by the patient at rest, during activity and at palpation (performed by the Investigator or the study nurse).
- Weight-Bearing using a Likert scale (see details in Annex 3): in this study, functionality on the affected limb will be assessed using weight-bearing. In this test, the patient will be asked to place only as much weight as he/she feels comfortable (as tolerated) on the injured limb (based on pain feeling) standing. This specific category allows a differential scoring related to pain feeling.

#### 2.4.3 Radiological Evaluation – TUS and mRUS

In this study, the modified Radiographic Union Score (mRUS) and Tomographic Union Score (TUS) will be assessed both on conventional X-ray and on CT scan, respectively. CT scan is more sensitive, and three-dimensional reconstruction will allow to have a more global view of the fracture and to improve the assessment (see details in section 3.2.2 and Annex 4).

**ALLOB-DU1 - Clinical Study Protocol**

ALLOB-DU1_CSP	V 05	Author: [name]	February 02, 2017	Pg. 40/136
---------------	------	-------------	-------------------	------------

## 2.5 Patient inclusion scheme

With the objective of maximum 32 patients treated in the study, and taking into account 10% drop-out, 35 patients will be enrolled.

For the first 16 patients, the patient recruitment will proceed stepwise by blocks of 4. Full first 2 weeks safety data of the first block of 4 patients will be analysed before the first patient of the second block of 4 patients is treated. First 48 hours safety data of the second block of 4 patients will be analysed before treating the first patient of the next block. This latter scheme will be repeated until the first 16 patients have been treated.

A Data Safety Monitoring Board (DSMB) will be established to assess the safety and efficacy when 6-month post treatment results for the first 16 assessable patients will be available (i.e., interim analysis). This Board will recommend to the Sponsor whether to continue, modify or stop the trial. The study can be prematurely stopped:

- For safety concerns
- For futility if less than 4 successes are observed
- For efficacy if 12 or more successes are observed

Additional patients can otherwise be treated in order to reach a total of 32 patients.

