**Interim Analysis**

A Data Safety Monitoring Board (DSMB) will be established to analyse and report the safety and the efficacy data when 6-month post-treatment results from the first 16 assessable patients will be available. This Board will recommend whether to continue, modify or stop the study. If success is less than 30% or higher than 70%, patient recruitment will be stopped. If the DSMB recommendation is continuation (with or without changes) of the study, patient recruitment will continue until 32 patients have been treated.

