#### 10.5.1.2 *Type I error rate, significance tests*

In this study, two sided tests will be performed at a 5% level of significance except for efficacy analyses.

According to the Schoenfeld approach (Schoenfeld *et al.*, 1980), for the efficacy analysis, the type I error rate will be increased from the usual 5% to the 10% rate. Indeed, in this pilot single arm “proof of concept” study, it is appropriate to maintain the power and increase the type I error rate. This increases the risk of erroneously concluding that the treatment is worthy of further investigation, but does not increase the risk of missing an efficacious treatment. So in

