10.5.8 Interim data analysis10.5.8.1 *Efficacy Assessment*

At Month 6, the efficacy assessment will be based on:

- The patient had a rescue surgery

Or

- The Global Disease Evaluation score (VAS) as perceived by the patient has not improved by at least 25% *and* the TUS as assessed by CT scan has not increased by at least 2 points (versus baseline).

For rescue surgery, based on the efficacy of the treatment, Investigators will have the opportunity to switch to rescue surgery from Month 3 if the patient has not improved by at least 15% his/her global disease evaluation score (VAS) as perceived by the patient and his/her mRUS or TUS, as available, has not improved by 1 point.

The levels of improvements have been calculated as based on other similar impaired fracture healing trials (e.g., PREOB® on non-union fracture) and take into account standard deviation and patient variability.

10.5.8.2 *Presentation of the 2-stage design*

The main objective of this phase I/II-a non-comparative sequential design is to assess the interest presented by this new treatment without performing a comparative study that allows identifying only small differences of efficacy between the new treatment and a control, what requires a relatively high number of subjects. The principle of a sequential design is to perform the study in two or more stages in order to minimize the number of patients exposed to an ineffective treatment to conclude in a more premature way.

The most appropriate sequential method for this study is the 2-stage Fleming plan. In this design, the efficacy criterion is a binary criteria of “success/failure” type, with  $p_0$  as the superior limit of ineffectiveness (maximum value below which the new treatment is considered as being ineffective) and  $p_1$  as the inferior limit of efficacy (minimum value above which the new treatment is considered as being effective). The null and alternative test hypotheses are the following:

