## ALLOB-DU1 - Clinical Study Protocol

ALLOB-DU1\_CSP

V 05

Author: [name]

February 02, 2017

Pg. 103/136

- $H_0: p \leq p_0$

- $H_1: p \geq p_1$

Using  $\alpha$  = the type I error and  $\beta$  = the type II error

The tested hypotheses are as follows:

- $H_0$  : a success rate  $\leq 30\%$  is uninteresting ( $p_0=0.30$ )
- $H_1$  : a success rate of at least  $70\%$  is expected ( $p_1=0.70$ )

Using  $\alpha = 0.05$  and  $\beta = 0.20$

In the case of a two-stages Fleming plans, the study can be stopped for ineffectiveness (if the number of successes is lower than a computed limit) or for efficacy (if the number of successes is  $\geq$  a computed limit).

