#### 10.5.8.3 Results of the computing

According to the 2 stages Fleming method, 20 treated patients are required (type I error rate  $\alpha$  of 5% and a statistical power of 80%). Taking into account that patients are enrolled by cohort of 4 and considering the potential heterogeneity of the population, 32 patients in total will be enrolled and treated in the study.

Step	Nb. of patients/step	Cumulated Nb. of patients	Treatment ineffective if $\Pi < 0.30$	Treatment effective if $\Pi > 0.70$
1	16 (assessable)	-	Number of successes $\leq 4$	Number of successes $\geq 12$
2	Up to 16 (assessable)	32	n.a.	n.a.

For the first 16 assessable patients, an interim analysis will be performed at the end of the 6 months follow-up (Visit #6).

The study will be prematurely stopped for:

- Safety concerns

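### The stage-1 efficacy limit of 12 out of 16 is an observed 70% cut-off, not the limit that the named Fleming design gives, and it weakens early stopping

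*Combined protocol and SAP*

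**What the plan says.** Section 10.5.8.2 names the design: "The most appropriate sequential method for this study is the 2-stage Fleming plan". It sets p0 = 0.30, p1 = 0.70, alpha 0.05 and beta 0.20, and explains that "the study can be stopped for ineffectiveness (if the number of successes is lower than a computed limit"), with a corresponding computed limit for efficacy.

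Section 10.5.8.3 reports the result: "According to the 2 stages Fleming method, 20 treated patients are required", at 5% type I error and 80% power. The total was then raised to 32, for cohorts of four and heterogeneity of the population. Its table gives, for 16 assessable patients at stage 1, ineffective at 4 or fewer successes and effective at 12 or more. The column headings tie these to proportions below 0.30 and above 0.70. The stage-2 limits are shown as not applicable.

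Three other places bear on the limits:
- Section 2.5 allows a stop "For efficacy if 12 or more successes are observed". It and the list after the table in 10.5.8.3 keep 12 for efficacy but put futility at fewer than 4.
- The synopsis, under Interim Analysis, states the rule as observed rates: "If success is less than 30% or higher than 70%, patient recruitment will be stopped".
- Section 10.5.1.2 says that for the efficacy analysis "the type I error rate will be increased from the usual 5% to the 10% rate", which conflicts with the 5% used for the design.

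**The concern.** A reader takes 4 and 12 to be Fleming boundaries for the stated hypotheses and error rates. They look instead like 30% and 70% of 16. The values p0 and p1 describe the true success rate. A stopping boundary is a count chosen so that the whole two-stage rule has the required error rates, and it need not fall at either value.

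What is at stake is the interim decision. The data safety monitoring board would apply a threshold in the belief that it carries the properties of the named method. Section 10.5.8.2 justifies a staged design by limiting exposure to an ineffective treatment and by reaching a conclusion sooner. Limits set further out than the method requires work against both aims.

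**Working it through.** **Inputs.** n1 = 16, n2 = 16, N = 32 (10.5.8.3); p0 = 0.30, p1 = 0.70 (10.5.8.2); alpha 5% (10.5.8.2 and 10.5.8.3) or 10% (10.5.1.2). The null hypothesis p ≤ p0 implies a one-sided test. One-sided 2.5% is added in case a two-sided 5% was meant. N = 20 is also tried, because 10.5.8.3 calls it the required size.

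**Reproducing the printed limits.** 0.70 × 16 = 11.2, so the smallest count above 70% is 12 (11/16 = 68.75%). 0.30 × 16 = 4.8, so the largest count below 30% is 4 (5/16 = 31.25%). The synopsis rule gives the table's limits exactly. It does not give the text's fewer than 4.

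**Fleming's formulas**, with z = z(1−alpha):
- efficacy limit r1 = round[n1·p0 + z·√(N·p0·(1−p0))] + 1
- pA = (√(N·p0) + z·√(1−p0))² / (N + z²)
- futility limit a1 = round[n1·pA − z·√(N·pA·(1−pA))]
- final limit r2 = round[N·p0 + z·√(N·p0·(1−p0))] + 1

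**N = 32, alpha 5% (z = 1.645):**
- r1: 4.8 + 1.645 × √6.72 = 9.06, rounded to 9, plus 1 = **10**
- pA = (3.098 + 1.376)² / 34.71 = 0.577
- a1: 9.23 − 1.645 × √7.81 = 4.63, rounded to **5**
- r2: 9.6 + 4.26 = 13.86, rounded to 14, plus 1 = **15**

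**All settings tried, n1 = 16:**

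| N | one-sided alpha | efficacy at or above | futility at or below (unrounded) |
|---|---|---|---|
| 32 | 10% | 9 | 5 (4.65) |
| 32 | 5% | 10 | 5 (4.63) |
| 32 | 2.5% | 11 | 5 (4.66) |
| 20 | 10% | 8 | 6 (6.33) |
| 20 | 5% | 9 | 7 (6.79) |
| 20 | 2.5% | 10 | 7 (7.21) |

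The efficacy limit runs from 8 to 11 and is never 12. Twelve appears only with N = 32 at a one-sided alpha of about 1%, which the protocol does not state.

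**Exact binomial stopping probabilities at stage 1:**

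| True p | Event | Printed limits | Fleming, 5%, 16 + 16 |
|---|---|---|---|
| 0.70 | efficacy stop | 0.450 (≥ 12) | 0.825 (≥ 10) |
| 0.30 | futility stop | 0.450 (≤ 4) or 0.246 (< 4) | 0.660 (≤ 5) |
| 0.50 | any stop | 0.077 (≤ 4) or 0.049 (< 4) | 0.332 |

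**Overall error rates.** The protocol gives no stage-2 limit, so 15/32 is assumed here for both sets:
- printed limits: alpha 0.032 (≤ 4) or 0.033 (< 4), power 0.998
- Fleming limits 5/10/15: alpha 0.034, power 0.997
- Fleming limits at 10% (5/9/14): alpha 0.072

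**Expected sample size** = 16 + 16 × P(continue), if nobody beyond the first 16 is treated before the interim decision:
- p = 0.70: printed (≤ 4, ≥ 12) 16 + 16 × (1 − 0.450) = 24.8; Fleming 16 + 16 × (1 − 0.826) = 18.8
- p = 0.30: printed 16 + 16 × (1 − 0.450) = 24.8 (≤ 4) or 16 + 16 × (1 − 0.246) = 28.1 (< 4); Fleming 16 + 16 × (1 − 0.667) = 21.3

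**The case against.** **The rule is disclosed and cautious.** The synopsis states the 30%/70% rule openly, and a strict efficacy stop is defensible in a small pilot study whose primary objective includes safety. A Fleming limit would declare efficacy at 10/16 (62.5%), or at 9/16 (56%) with alpha 10%, below the 70% that the protocol calls effective. This stands as a reason why a sponsor might choose 12. It does not support saying that the Fleming computation produced 12.

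**Error rates are not harmed.** A reader might infer that a wrong boundary inflates type I error or costs power. It does neither: with a final limit of 15/32, alpha and power are within the stated 5% and 80%. A reader might also set P(12 or more of 16 | p = 0.30) = 0.0003 against 5%. That is not like for like, because an interim limit is not meant to spend the whole alpha; 10/16 itself spends only 0.007.

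**The futility limit in the table is close.** The formula gives 4.63 for 16 + 16, and the protocol states no rounding rule. Rounding down gives the table's 4. This stands. Fewer than 4 in the text has no such support, and it accounts for much of the widest gap (25% against 66%).

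**The corrected limits are not unique.** They depend on alpha and on whether N is 20 or 32, so no single set can be imposed yet. This also stands.

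**The patient savings may not be realised.** Section 8.2.4 lets recruitment run on towards 32 after the fourth safety block, and sections 8.3.4, 10.2 and 10.10 provide for data on patients enrolled beyond the first 16. With a 6-month endpoint, some stage-2 patients may be treated before the boundary is read. The synopsis can be read the other way, with recruitment continuing only after the board's recommendation, so the point is open.

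**Conclusion.** The stage-1 efficacy limit is attributed to a method that does not produce it under any alpha or N in the protocol. It is an observed-rate cut-off placed at p1. The table's futility limit can be explained by rounding down; the text's version cannot, and the two contradict each other.

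The consequence is weaker early stopping, measured against the 16 + 16 Fleming limits at one-sided 5%. With the table's limits the study continues to stage 2 in about 55% of cases at either hypothesis. Only the fewer-than-4 reading at p = 0.30 raises this to 75%, so it would be too strong to say that the study nearly always runs to 32. The differences in expected size (24.8 against 18.8 at p = 0.70; 24.8 to 28.1 against 21.3 at p = 0.30) are upper figures: they hold only if treatment pauses at 16, and any treatment before the interim shrinks them.

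The limits should be corrected or re-described before they are used. The validity of the final efficacy conclusion is not threatened by this point.

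**What to change.** First settle the two inputs that the protocol leaves in conflict: alpha for efficacy (5% or 10%) and the N on which the boundaries rest (20 or 32). Then take one of two routes.

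1. **Use the Fleming limits.** Replace the limits in the 10.5.8.3 table and the list after it, in section 2.5 and in the synopsis. For 16 + 16 these are: at 5%, futility at 5 or fewer, efficacy at 10 or more and a final limit of 15/32; at 10%, 5 or fewer, 9 or more and 14/32. State the rounding convention.
2. **Keep 12 and 4 deliberately.** Describe them as observed 70%/30% cut-offs, remove the attribution to Fleming, reconcile 4 or fewer with fewer than 4, supply the final limit, and report the actual alpha, power and stopping probabilities.

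Under either route, state whether patients beyond the first 16 may be treated before the interim decision, since the saving from early stopping depends on it.

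The cost is a recalculated table and matching wording in the places named, through a protocol amendment and the SAP. No patients or visits are added.

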## 2.6 Study Population

### 2.6.1 Eligibility

Prior to patient inclusion and baseline assessment by the Investigator, a screening period is planned to allow verification of patient eligibility.

Patients will be selected based on the eligibility criteria listed in section 2.6.

#### *Duration of delayed-union*

As the trial involves patients diagnosed with delayed-union fractures of a long bone (see 2.4.1) at the time of inclusion, and as the time between screening and implantation could take up to 8 weeks, delayed-union patients could be screened (Visit #1) as from a fracture duration of 3

## ALLOB-DU1 - Clinical Study Protocol

ALLOB-DU1\_CSP

V 05

Author: [name]

February 02, 2017

Pg. 41/136

[figure not shown]
months  $\pm$  2 weeks to a maximum of 7 months  $\pm$  2 weeks. Patients will be treated up to 8 months  $\pm$  2 weeks after fracture occurrence.

*Revision of osteosynthesis material*

Osteosynthesis revision is allowed prior to patient entry into the study:

- With a minimum of 2 months between revision/surgery and screening for revision/surgery performed at the fracture site
- With a minimum of 4 weeks between revision/surgery and screening for revision/surgery outside the fracture site.

Before implantation, the absence of signs of radiological healing (due to the osteosynthesis revision performed before the study) will be confirmed by the Independent Radiologist. This will be done by comparing the images from conventional X-Ray (and/or CT scan) performed at Visit #1 with the X-Ray (and/or CT scan) performed before the study (a minimum of 4 weeks between the images is required).

*Patient Information*

Apart from inclusion and exclusion criteria detailed in section 2.6.2 and 2.6.3, the following clinical information and data will also be collected and recorded:

- Past and current relevant medical (and surgical) history

**ALLOB-DU1 - Clinical Study Protocol**

ALLOB-DU1_CSP	V 05	Author: [name]	February 02, 2017	Pg. 42/136
---------------	------	-------------	-------------------	------------

- Alcohol consumption (including the number of drinks per day)
- Smoking habits (including the number of cigarettes, cigars, and/or pipes per day)

Patients will not be selected according to their gender, since there are no known or expected gender differences in pharmacokinetics, efficacy, and/or safety profile of the test product, no subgroup analysis with sex as a variable is planned (random sex distribution).

#### ***2.6.2 Inclusion Criteria***

All subjects must satisfy ALL the following criteria at study entry:

- Patient aged 18 to 80 years inclusive
- Patient diagnosed with a non-infected delayed-union fracture of a long bone (femur, tibia, fibula, humerus, ulna, radius) of minimum 3 months and maximum 7 months ( $\pm$  2 weeks) without signs of healing over the last 4 weeks at the time of screening
- Modified Radiographic Union Score (mRUS) < 10
- Global Disease Evaluation Score as assessed by the patient  $\geq$  20 mm on a Visual Analogue Scale
- Patient (or patient's legally acceptable representative) capable to provide a written, dated, and signed informed consent prior to any study procedure.

#### ***2.6.3 Exclusion Criteria***

The following criteria should be checked at the time of study entry. If ANY exclusion criterion applies, the patient must not be included in the study:

##### *Current symptoms and/or signs related to the disease under study*

- Fracture interline  $>$  2.5 cm, as defined by the Independent Radiologist
- Insufficient reduction of the fracture

---

 In case the mRUS is not assessable, the Tomographic Union Score (TUS) could be used instead (judged by the Independent Reader)

**ALLOB-DU1 - Clinical Study Protocol**

ALLOB-DU1_CSP	V 05	Author: [name]	February 02, 2017	Pg. 43/136
---------------	------	-------------	-------------------	------------

- Insufficient fracture stability defined as osteolysis at the level of the nails/screws and/or defect and/or mobility of the osteosynthesis material at physical examination, as assessed by the Investigator
- Osteosynthesis material revision or surgery (i) performed less than 2 months from the screening visit at the fracture site *or* (ii) performed less than 4 weeks from the screening visit at distance of the fracture site.
- Active bone infection (at site)
- Femoral neck fracture, if the femur is the target bone of the study
- Multifocal fracture (e.g., more than one fracture site on the studied bone)
- Symptomatic delayed/non-union fracture on the neighbouring bone , as judged by the Investigator
- Severe nerve damage and/or neuropathic/neuropathic-like pain at fracture site, that may interfere with assessment during the study, as appreciated by the Investigator
- Severe tendon lesion (e.g., rupture or enthesopathy) at fracture site, that may interfere with assessment during the study, as appreciated by the Investigator

*Current or previous diagnoses, signs and/or symptoms*

- Positive serology for HIV (defined as positive Anti-HIV 1 and/or 2 and/or positive PCR)
- Active hepatitis B (defined as positive HBs Ag and/or positive PCR)
- Active hepatitis C (defined as positive Anti-HCV and/or positive PCR)
- Global sepsis
- Renal impairment, defined as serum creatinine >2 mg/dl or 176 µmol/L
- Hepatic impairment, defined as alanine aminotransferase or aspartate aminotransferase  $\geq$  3 times the upper normal limit
- Poorly controlled diabetes mellitus (defined as HbA1C >8%)
- Known allergy to gentamicin
- History of hypersensitivity to human biological material including blood and blood derived products, documented clinically or by laboratory tests

